9.4.3 Inclusion criteria Part III: SSc patients

1. Willing and able to give written informed consent for participation in the study.
2. Male and female SSc patients aged 40-75 years inclusive.
3. SSc disease duration less than 60 months based on the time from the first non-Raynaud phenomenon manifestation.
4. Systemic Sclerosis diagnosed according to European League Against Rheumatism (EULAR)/American College of Rheumatology (ACR) criteria [24].
5. Raynaud's Phenomenon as determined by the investigator, and with a typical frequency of attacks during the winter months of on average 5 per week (re-confirmed on admission to the study unit Day-1).
6. WOCBP must practice abstinence (only allowed when this is the preferred and usual lifestyle of the subject) or must agree to use a highly effective method of contraception with a failure rate of < 1% to prevent pregnancy (combined [oestrogen and progestogen containing] hormonal contraception associated with inhibition of ovulation [oral, intravaginal, transdermal], progestogen-only hormonal contraception associated with inhibition of ovulation [oral, injectable, implantable], IUD or IUS) from at least 4 weeks prior to dose to 4 weeks after last dose. Their male partner must agree to use a condom during the same time frame.

Women of non-childbearing potential are defined as pre-menopausal females who are sterilised (tubal ligation or permanent bilateral occlusion of fallopian tubes); or post-menopausal defined as 12 months of amenorrhea (in questionable cases a blood sample with simultaneous detection of FSH 25-140 IE/L and oestradiol <183 pmol/l is confirmatory).

Male subjects must be willing to use condom or be vasectomised or practice sexual abstinence to prevent pregnancy and drug exposure of a partner and refrain from donating sperm from the date of dosing until 3 months after dosing with the IMP.

Their female partner of child-bearing potential must use contraceptive methods with a failure rate of < 1% to prevent pregnancy (see above).

9.4.4 *Exclusion criteria part III: SSc patients*

1. Females who are breast feeding or plan to be pregnant.
2. Positive serum or urine pregnancy test (minimum sensitivity 25 IU/L or equivalent units of HCG) at screening and within 24 h prior to the first administration of IMP.
3. Mixed connective tissue disease or "overlap" (i.e. those who satisfy more than one set of ACR criteria for a rheumatic disease).
4. Ongoing treatment with immunosuppressive therapies including, but not restricted to; cyclophosphamide, azathioprine, mycophenolic acid, methotrexate, or cyclosporine, or use of those medications within 4 weeks prior to first dose.
5. Use of inhaled or systemic corticosteroids within 4 weeks prior to first dose.
6. Use of iloprost within 4 weeks prior to first dose.
7. Concurrent serious medical condition which in the opinion of the investigator makes the patient inappropriate for this study such as uncontrollable Congestive heart failure, significant arrhythmia, severe pulmonary or systemic hypertension, severe gastrointestinal (GI) involvement, significant hepatic impairment, serum creatinine of greater than 2.0, active infection, severe diabetes, unstable atherosclerotic cardiovascular disease, malignancy, or severe peripheral vascular disease. Ongoing DUs are allowed at the discretion of the Investigator but must not need iloprost treatment and should not be infected.
8. Have known allergies to any components of the GS-248 formulation.
9. Use of NSAIDs (including e.g. coxibs and aspirin), antacids, PPIs or any medication that changes gastric pH within 2 weeks prior to the (first) administration of IMP.
10. Regular use of any prescribed or non-prescribed medication including analgesics, herbal remedies, vitamins and minerals within 2 weeks prior to the (first) administration of IMP, except hormonal contraception and occasional intake of paracetamol (maximum 2000 mg/day; and not exceeding 3000 mg/week) and nasal decongestants without cortisone, antihistamine or anticholinergics for a maximum of 10 days, at the discretion of the Investigator.
11. Any positive result on screening for HBsAg, HCVAb or HIV 1 and/or 2 antibodies.
12. Presence or history of drug or alcohol abuse or excessive intake of alcohol, as judged by the Investigator.
13. Any positive result for drug abuse and/or alcohol at screening or on admission to the unit prior to administration of the IMP.
14. Participation in another clinical study with an experimental drug within 3 months before the administration of IMP.
15. Consumption of grapefruit or grapefruit juice within 14 days of study drug administration.

16. Any clinically significant illness, medical/surgical procedure or trauma within 4 weeks of the first administration of IMP.
17. Malignancy within the past 5 years with the exception of in situ removal of basal cell carcinoma or resected benign colonic polyps.
18. Any planned major surgery within the duration of the study.
19. Prolonged QTcF (>450 ms), cardiac arrhythmias or any clinically significant abnormalities in the resting ECG at the time of screening, as judged by the Investigator.
20. Current smokers or users of nicotine products. Irregular use of nicotine (e.g. smoking, snuffing, chewing tobacco) less than 3 times per week is allowed before screening visit.
21. Unable or unwilling to reduce caffeine consumption to a daily intake of >5 cups of caffeine containing beverages.
22. Intake of xanthine and/or taurine containing energy drinks within 2 days prior to screening.
23. Plasma donation within one month of screening or blood donation (or corresponding blood loss) during the three months prior to screening.
24. Investigator considers the subject unlikely to comply with study procedures, restrictions and requirements.

9.5 Restrictions during the study

The subjects must be willing to comply to the below restrictions during the entire study duration *i.e.*, from screening to the end-of-study visit (or longer if specified).

9.5.1 *Restrictions all parts*

Contraception Requirements: All WOCBP must use effective contraception (defined in inclusion criterion No 3) or practice abstinence (only allowed when this is the preferred and usual lifestyle of the subject) from at least 4 weeks prior to dose until 4 weeks after last dose. Their male partners must agree to use a condom during the same time frame.

The male volunteers are expected to use condom and their female partner of child-bearing potential must use a contraceptive method with a failure rate of < 1% to prevent pregnancy (for details, refer to inclusion criterion No 3) and drug exposure of a partner and refrain from donating sperm from the date of dosing until 3 months after the last IMP administration.

Meals and Dietary Restrictions:

Part I: The IMP will be administered in the fasted state (at least 10 h of fasting) together with 240 mL of tap water.

Part II and Part III: On Day 1 and Day 10, the IMP will be administered in the fasted state (at least 10 h of fasting) together with 240 mL of tap water. On other dosing days, the IMP will be administered at the clinic just prior to breakfast.

Part IV: On Day 1 and Day 10, the morning dose will be administered in the fasted state (at least 10 h of fasting) together with 240 mL of tap water. From Day 2 (evening dose) to Day 9 (evening dose) there are no food restrictions in relation to intake of celecoxib. However, the IMP should be taken at approximately the same time (± 1 h) each morning and evening.

During residential stays, standardised meals will be served on PK/PD sampling days (24 h after dose on Day 1 [Part I], Day 1 and Day 10 [Part II, III and IV]). Breakfast will be served just after dose (except on Day 1 and Day 10 of Part II, III and IV) and lunch will be served 4 h post-dose. Snack, dinner and evening snack will be served approximately 7, 9 and 11 h post-dose, respectively. Water is allowed ad libitum at the clinic except 1 h before dose and 1 h after dose on PK and PD sampling days.

For details on IMP administration in terms of food restrictions, refer to Section 10.6.

Fasting: The subjects should be fasting overnight (10 h) before Day 1 of Part I and before Day 1 and Day 10 of Part II, III and IV until 4 h post-dose.

Alcohol: Consumption of alcohol is not allowed within 48 h prior to the screening visit and all subsequent visits to the clinic including the end-of-study visit of each part. In addition, consumption of alcohol is disallowed during residential stays.

Coffee: Not more than 5 cups of coffee per day is allowed during the study from screening to end-of-study visit of each part.

Xanthine or taurine containing products/beverages: Energy drinks (e.g. Redbull) are not allowed during the study from screening until the end-of-study visit of each part.

Nicotine: Smoking or use of nicotine-containing products is not allowed during the study from screening until the end-of-study visit of each part.

Grapefruit and grapefruit containing products: Consumption of grapefruit and/or grapefruit containing products, Seville oranges is not allowed during the study from 14 days prior to IMP administration until the end-of-study visit of each part.

Blood donation: The subjects must not donate blood or plasma during the study until 3 months after the final medical examination at the end-of-study visit of each part.

Participation in other clinical studies: Study subjects are not allowed to participate in any other interventional clinical study during the study period.

Exercise: Subjects will abstain from strenuous exercise for 72 h before each blood collection for clinical laboratory tests.

9.5.2 *Restrictions Part I, II and III*

Sun protection is required in Part I, Part II and Part III from the first administration of IMP until the end-of-study visit of each part to follow the recommendations given by Centres for Disease Control and Prevention (CDC): https://www.cdc.gov/cancer/skin/basic_info/sun-safety.htm:

- Stay in the shade, especially during peak hours of 10 AM to 4 PM.
- Wear clothing that covers arms and legs
- Use a hat or cap that shades the face, head, ears and neck
- Wear sunglasses that block both ultraviolet A (UVA) and ultraviolet B (UVB) rays
- Proper use of a broad-spectrum sunscreen with a sun protection factor (SPF) of 15 or higher.
- Abstain from use of tanning beds.

9.5.3 *Prior and concomitant therapy*

9.5.3.1 *Prohibited medication Part I, II and IV*

Use of any prescribed or non-prescribed medication including corticosteroids (inhaled and systemic), NSAIDs (including e.g. coxibs and aspirin), antacids, PPIs or any medication that changes gastric pH, herbal remedies, vitamin supplements and minerals and other over-the-counter (OTC) medicines is prohibited within 14 days of IMP administration until the end-of-study visit of each part.

9.5.3.2 *Prohibited medication Part III*

Use of iloprost or corticosteroids (inhaled and systemic) is disallowed from 4 weeks prior to the first IMP administration until the end-of-study visit as are treatment with other immunosuppressive therapies including, but not restricted to, cyclophosphamide, azathioprine, mycophenolic acid, methotrexate, or cyclosporine.

Use of any prescribed or non-prescribed medication including NSAIDs (including e.g. coxibs and aspirin), antacids, PPIs or any medication that changes gastric pH, herbal remedies, vitamin supplements and minerals and other OTC medicines is prohibited within 14 days of IMP administration until the end-of-study visit of each part.

9.5.3.3 *Allowed medication (all parts)*

- Paracetamol in doses up to 4000 mg/day for a maximum of 3 consecutive days. If this amount of paracetamol is not sufficient for treatment of the subjects, withdrawal should be considered.
- Nasal decongestants without cortisone, antihistamine or anticholinergics for a maximum of 10 days.

Other medications considered necessary for the subject's safety and wellbeing may be given at the discretion of the Investigator during the residential period. Following consultation with

the Sponsor, the Investigator will determine whether or not the subject should continue in the study.

9.6 Screening failures

Screening failures are defined as subjects who consent to participate in the clinical study but are not subsequently randomised in the study. A minimal set of screening failure information is required to ensure transparent reporting of screening failure subjects. Minimal information includes documentation of signed and dated ICF and reason(s) for screening failure.

Subjects/patients who do not meet the criteria for participation in this study may be re-screened.

Re-screening can be performed once if any of the following were reasons for screening failure or non-randomisation (as judged by the Investigator):

- Practical reasons.
- No significant medical conditions (e.g. influenza, nasopharyngitis).
- Reserve subject in previous cohort.
- Plasma or blood donation outside allowed time windows.

For subjects who are re-screened, a new screening number will be assigned and a new, signed ICF will be collected.

9.7 Subject/patient withdrawal

9.7.1 *General withdrawal criteria*

Subjects/patients are free to discontinue their participation in the study at any time and for whatever reason without affecting their right to an appropriate follow-up investigation or their future care. If possible, the reason for withdrawal of consent should be documented.

Subjects/patients may be discontinued from the study at any time at the discretion of the Investigator for any of the following reasons:

- Severe non-compliance to study protocol procedures, as judged by the Investigator and/or Sponsor
- Subject/patient is lost to follow-up
- Significant AEs posing a risk for the subject/patient, as judged by the Investigator and/or Sponsor
- Withdrawal of informed consent to the use of biological samples
- Pregnancy

Meeting of an exclusion criterion during the study, which, in the opinion of the Investigator, may pose a risk for the subject/patient.

9.7.2 *QTc withdrawal criteria*

A subject meeting the criteria below will be withdrawn from the study. The same QT correction formula will be used to determine discontinuation throughout the study.

- $QTcF > 500$ ms
- Change from baseline (i.e. the last measurement prior to the first dose) $QTc > 60$ ms

Withdrawal decisions will be based on an average QTc value of triplicate ECGs. If an ECG demonstrated a prolonged QT interval, two more ECGs will be obtained over a brief period and the averaged QTc values of the three ECGs used to determine whether the subject should be discontinued from the study.

9.7.3 *Liver chemistry withdrawal criteria*

Liver chemistry threshold stopping criteria have been designed to assure subject safety and to evaluate liver event aetiology. Study treatment will be stopped if any of the following liver chemistry stopping criteria, defined in the FDA Guidance on Drug-Induced Liver Injury [25], is met:

- Alanine aminotransferase (ALT) $3 \times$ Upper Limit of Normal (ULN) and total bilirubin $\geq 2 \times$ ULN ($>35\%$ direct bilirubin); **or** ALT $3 \times$ ULN and INR > 1.5)

NOTE: plasma bilirubin fractionation will be performed. Bilirubin is also measured via urine dipstick (a measurement of direct bilirubin, which would suggest liver injury).

- ALT $5 \times$ ULN.
- ALT $3 \times$ ULN if associated with symptoms (new or worsening) believed to be related to hepatitis (such as fatigue, nausea, vomiting, right upper quadrant pain or tenderness or jaundice) or believed to be related to hypersensitivity (such as fever, rash or eosinophilia).

Subjects with ALT $3 \times$ ULN **and** $< 5 \times$ ULN **and** bilirubin $< 2 \times$ ULN, who do not exhibit hepatitis symptoms or rash, will be allowed to continue study treatment as long as they are monitored weekly for four weeks.

9.7.4 *Procedures for discontinuation of a subject/patient from the study*

A subject who prematurely discontinues participation in the study will always be asked about the reason(s) for discontinuation and the presence of any AEs. If a subject withdraws consent, the investigator must ask the subject if he/she is willing, as soon as possible, to be assessed according to the procedures scheduled for the end-of-study visit in each part. Any ongoing AEs will be followed as described in Section 11.3.1.14.

The primary reason for discontinuation/early withdrawal must be specified in the eCRF and final drug accountability must be performed.

9.7.5 *Subject/patient replacement*

Part I: Based on recommendations given by the iSRC and as decided by the Sponsor, subjects who were randomised but not dosed may be replaced.

Part II, III and IV: Based on recommendations given by the iSRC and as decided by the Sponsor, subjects/patients who were randomised but not dosed may be replaced as may subjects who were prematurely withdrawn from the study for any reason except the occurrence of AEs assessed at least possibly related to the IMP.

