| Pregnancy Test (WOCBP) ⁵ | X | X | | | | | X | | | | X |
| Physical Examination | X | | X ^{6,7} | | | | | | | X ⁶ | X |
| Clinical Laboratory Profile ⁸ | X | X | | X ⁹ | X | X ⁹ | X | | | X | X |
| Vital signs ¹⁰ | X | X | X ¹¹ | X ¹¹ | X | | X | X ¹¹ | X ¹¹ | X | X |
| Body temperature | | | X ⁷ | | | | | X ⁷ | | | |
| 12-lead ECG | X | | X ^{7, 11} | X | X | | | X ^{7,11} | | X | X |
| Randomisation | | | X | | | | | | | | |
| IMP administration ¹² | | | X | X | X | X | X | X | | | |
| PK blood sampling | | | X ¹¹ | X ¹¹ | | X ¹⁴ | X ^{11, 14} | X ^{11, 14} | X | X | |
| Blood sampling for GS-248 MIST ¹³ | | | X ¹¹ | X ¹¹ | | | | X ¹¹ | X ¹¹ | | |
| Blood sampling for WBA | | | X ¹¹ | X ¹¹ | | | | X ¹¹ | X ¹¹ | | |
| Blood sampling for ADMA analysis | | | X ¹¹ | X ¹¹ | | | | X ¹¹ | X ¹¹ | | |
| Blood sampling for future biomarker analyses ¹⁵ | | | X ¹¹ | X ¹¹ | | | | X ¹¹ | X ¹¹ | | |

| | Screening | Residential period | | | | Daily visits | Residential period | | | | End-of-study | |
|-----------------------------------|-------------------|----------------------|-----------------|-------|-------|--------------|----------------------|-----------------|--------|--------|--------------|--|
| Visit | Visit 1 | Visit 2 ¹ | | | | Visit 3 to 7 | Visit 8 ¹ | | | | Visit 9 | |
| Assessment | Day -28 to Day -2 | Admission Day -1 | Day 1 | Day 2 | Day 3 | Day 4 to 8 | Admission Day 9 | Day 10 | Day 11 | Day 12 | Day 19 (±2) | |
| Urine collection | | X ¹⁶ | | | | | | X ¹⁶ | | | | |
| Meals ¹⁷ | | X | X | X | X | | X | X | X | X | | |
| Baseline symptoms | X | X | | | | | | | | | | |
| AEs and SAEs | | | X ¹⁸ | | | | | | | | | |
| Prior and concomitant medications | | X | | | | | | | | | | |

1. Details in separate flow chart (Table 8.1-4). The duration of the residential period may be amended following review of data from earlier cohorts.
2. Confirmation of eligibility prior to randomisation. Day -1 or Day 1.
3. Weight only.
4. Random drug screening test may also be performed at the discretion of the investigator.
5. WOCBP only. Screening: plasma/serum tests, other visits: urine test.
6. Short version of physical examination on Day 1 and Day 12.
7. Pre-dose assessments may be performed pre-dose Day 1/Day 10 or on Day -1/Day 9.
8. Clinical chemistry, haematology, coagulation, urinalysis (dip-stick), see Section 11.3.6.

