9. Clinical chemistry only on Day 2 and Day 6. Approximately 8 h post-dose on Day 2 and pre-dose on Day 6. No clinical laboratory sampling on Day 4, 5, 7 and 8.
10. Blood pressure and pulse, see Section 11.3.3.
11. For timing of assessments, refer to Table 8.1-4.
12. Once daily administration of IMP. On Day 1 and Day 10, administration under fasting conditions, i.e. fasting for 10 h before IMP administration until 4 h post administration. On Days 2 to 9, administration prior to breakfast at the same time each morning (±1 h).
13. Includes sampling for future exploratory analyses of potential GS-248 metabolites.
14. Pre-dose PK samples on Day 8, 9 and 10 must be taken within 5 minutes before dose.
15. Future exploratory analyses of biomarkers e.g. inflammatory biomarkers.
16. Urine for analysis of AA metabolites and for future analysis of GS-248 metabolites and biomarkers will be collected at the following intervals: 0 to 6 h, 6 to 12 h and 12-24 h post administration of study drug on Day 1 and Day 10. In addition, baseline urine is collected -24 h to -12 h and -12 h to 0 h prior to the first IMP administration on Day -1/Day 1.
17. Breakfast, lunch, snack, dinner and evening snack. Standardised meals during 24 h after dose on Day 1 and Day 10. For timing of meals, refer to Table 8.1-4. No breakfast on Day 1 and Day 10. Breakfast only on Day 3 and Day 12.
18. From administration of IMP.

Table 8.1-4 Detailed schedule of events for Visit 2 and Visit 8, Part II (MAD)

| Assessment/time-point | Day -1 | Day 9 | Day 1/Day 10 | | | | | | | | | | | Day 2/Day 11 | | Day 3/Day 12 |
|--|-----------------|-----------------|--------------------|-------|------|----|----|----|--------------------|----|-----|-----|-----------------|-----------------|-----------------|--------------|
| | Admission | Pre-dose | 0 | 0.25h | 0.5h | 1h | 2h | 4h | 6h | 8h | 12h | 16h | 24h | 36h | 48 h | |
| Inclusion/exclusion criteria | | | X ¹ | | | | | | | | | | | | | |
| Pregnancy test (WOCBP) | X | X | | | | | | | | | | | | | | |
| Urine drug screen | X | X | | | | | | | | | | | | | | |
| Alcohol breath test | X | X | | | | | | | | | | | | | | |
| Physical examination | | | X ^{1,2} | | | | | | | | | | | | X ³ | |
| Clinical laboratory profile | X | X | | | | | | | | | | | X ⁵ | | X | |
| Vital signs ⁶ | X | X | X | | | | X | X | X | X | X | X | X | X | X | |
| Body temperature | | | X ⁴ | | | | | | | | | | | | | |
| 12-lead ECG | | | X ⁴ | | | | | X | | | X | | X ⁷ | | X | |

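### Section 9.7.3 both requires stopping and permits continuing when ALT is 3 to <5 × ULN, bilirubin <2 × ULN, no hepatitis symptoms or rash are present and INR is >1.5; INR is not scheduled with the Day 6 ALT

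*Protocol*

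**What the plan says.** **Stopping list.** Protocol Section 9.7.3 opens with "Study treatment will be stopped if any of the following liver chemistry stopping criteria" is met. Three listed items matter here:

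- The INR criterion, "ALT $3 \times$ ULN and INR > 1.5", carries no bilirubin or symptom condition.
- ALT at 3 × ULN with symptoms of hepatitis, "such as fatigue, nausea, vomiting, right upper quadrant pain or tenderness or jaundice".
- ALT at 3 × ULN with symptoms "believed to be related to hypersensitivity (such as fever, rash or eosinophilia").

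**Continue paragraph.** The section closes with subjects whose ALT is between 3 and 5 × ULN, whose bilirubin is below 2 × ULN and "who do not exhibit hepatitis symptoms or rash, will be allowed to continue study treatment", provided they are monitored. INR, fever and eosinophilia are not mentioned.

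**Laboratory schedule.** For Part II, footnote 8 of Table 8.1-3 defines the full profile: "Clinical chemistry, haematology, coagulation, urinalysis (dip-stick), see Section 11.3.6". Footnote 9 of the same table says "Clinical chemistry only on Day 2 and Day 6", and then "No clinical laboratory sampling on Day 4, 5, 7 and 8". Table 8.1-5 says the same for Part III. Table 11.3-1 places INR under coagulation and the leucocyte differential, including eosinophils, under haematology.

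**The concern.** The liver is the organ that limits exposure in this trial. Section 6.4 says that the hepatobiliary findings in dogs set the limits for human exposure, and Section 6.7 relies on liver biomarker monitoring so that dosing can be stopped in individuals. The rule that turns a laboratory result into an individual decision should therefore give one answer for one set of results.

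For a definable group of subjects it gives two. An assessor who stops follows the list, and an assessor who continues can point to a paragraph that describes the subject's ALT band and bilirubin and permits it. Identical results could then be handled differently on different occasions or by different assessors.

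The schedule adds a second difficulty. On Day 6, ALT is measured without the INR and eosinophil count that some of the stopping criteria need.

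**Working it through.** No figure in the plan can be reproduced here; this is a comparison of clauses and a reading of the schedule.

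**Step 1. Clauses side by side, for ALT 3 to <5 × ULN.** The inequality sign before the ALT multiples is missing in the text available. I read it as at or above, and the overlap does not depend on that choice.

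| Feature | Stopping list | Continue paragraph |
|---|---|---|
| Bilirubin ≥2 × ULN (>35% direct) | stop | excluded |
| Hepatitis symptoms | stop | excluded |
| Rash (hypersensitivity) | stop | excluded |
| INR >1.5 | stop | not mentioned |
| Fever (hypersensitivity) | stop | not mentioned |
| Eosinophilia (hypersensitivity) | stop | not mentioned |

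The first three rows agree and the last three do not. A hypothetical subject with ALT 4 × ULN, bilirubin 1 × ULN, no symptoms and INR 1.8 satisfies both clauses.

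**Step 2. Count of combinations.** Six yes/no features give 2^6 = 64 combinations in this ALT band. The continue paragraph fixes three of them (bilirubin <2 × ULN, no hepatitis symptoms, no rash), leaving 2^3 = 8. Among those 8:

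- Plain reading, with fever and eosinophilia taken as believed related to hypersensitivity: only the combination with none of INR >1.5, fever and eosinophilia avoids the stopping list. Conflicts: 8 − 1 = 7.
- Narrowest reading, counting INR only: conflicts are the combinations with INR >1.5, which is 8 / 2 = 4.

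No combination in the band is left without a rule. These are counts of logical states. They are not probabilities, and the documents give no basis for estimating how often each would occur.

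**Step 3. Schedule in Part II during dosing (Days 1 to 10).**

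| Day | Sample | ALT | INR | Eosinophils |
|---|---|---|---|---|
| 2 | chemistry only, about 8 h post-dose | yes | no | no |
| 3 | full profile | yes | yes | yes |
| 6 | chemistry only, pre-dose | yes | no | no |
| 9 | full profile | yes | yes | yes |

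The Day 2 gap is closed by the Day 3 profile. The material gap follows Day 6: scheduled INR and differential are 9 − 3 = 6 days apart, and after a raised Day 6 ALT the next ones are due 9 − 6 = 3 days later. Section 9.7.3 specifies no INR or differential to be drawn in response to a raised ALT.

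**Step 4. Scope.** The planned Part III schedule is the same, but SAP Section 3.2 reports that Part III was cancelled. Part I is a single dose. Part IV has laboratory tests only at screening and end of study. The schedule point therefore concerns Part II, and Part III only as planned.

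**The case against.** The best reply is that the two clauses are not equal in force. Stopping is mandatory and triggered by any one criterion, whereas continuing is only allowed. Obeying the stopping list breaches nothing, and a sensible reader would take the permission to cover subjects who have met no stopping criterion. This stands in part: the protocol does not order two opposite actions. But the continue paragraph has its own, shorter list of exclusions for the same ALT band, and no sentence subordinates it to the stopping list.

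Second, the fever and eosinophilia cases depend on judgement. They count only if believed related to hypersensitivity, and both symptom lists are illustrative, so fever could be argued to be a hepatitis symptom. That stands. The INR case needs no such interpretation.

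Third, there are safeguards. Section 6.7 has the medical monitor reviewing individual subjects continuously and allows stopping even when the stopping rules are not fulfilled. Section 8.3.7 allows ad hoc meetings of the internal safety review committee (iSRC), which may recommend stopping individuals. Subjects also attend daily for dosing. This reduces the practical risk but does not settle which clause governs.

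Several stronger readings are tempting but unsupported:

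- *Different sites could apply the rule differently.* The documents describe one research clinic.
- *Missing dipstick bilirubin on Day 6 hides a criterion.* The dipstick result is not itself a listed criterion, and total and conjugated bilirubin are in the chemistry panel.
- *A set number of doses would be given with the criterion unassessed.* No laboratory turnaround time is stated and nothing forbids unscheduled tests, so no dose count follows.
- *The primary endpoints are compromised.* Those are adverse events and clinically significant changes, recorded whichever clause is followed; withdrawals are not among them.

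**Conclusion.** The point holds in a bounded form. Section 9.7.3 contradicts itself for subjects with ALT 3 to <5 × ULN, bilirubin <2 × ULN, no hepatitis symptoms and no rash. With INR >1.5 the conflict between required stopping and permitted continuation follows from the text as written. With fever or eosinophilia it rests on those signs being attributed to hypersensitivity.

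The schedule compounds this at one point in Part II, the chemistry-only Day 6 sample, with INR and eosinophils next scheduled on Day 9. The discretion of the medical monitor and the iSRC softens the consequence without resolving the text.

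The conclusion assumes that the ALT thresholds mean at or above the stated multiple. It says nothing about how many subjects were affected, which the documents do not show.

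**What to change.** The sponsor's clinicians should reconcile the stopping list and the continue paragraph of Section 9.7.3 with each other for INR, fever and eosinophilia, so that each set of results leads to one stated outcome. They should also reconcile the laboratory schedule in Tables 8.1-3 to 8.1-6 with the criteria that Section 9.7.3 requires to be assessed when ALT is raised. Which action is right, and which tests are drawn when, is for them to decide; no clinical rule is proposed here.

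SAP Section 3.4 reports 24 subjects already randomised and dosed in Part II. For this study, what remains is transparency: the study report should list any subject with ALT in the 3 to <5 × ULN band, the INR and eosinophil results available at that time, and the clause applied. The corrected text matters for any later protocol that reuses the section.

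The cost is protocol wording and one listing. If the clinicians choose to extend the Day 6 sample, it is added tests at an existing draw, with no new visit.
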